#### 8.3 Multicenter studies

No effects of centers will be evaluated in this study due to the small numbers at individual sites.

### 8.4 Multiple comparisons and multiplicity

A fixed sequential testing will be used in the sense that the key secondary efficacy endpoints will only be tested if the null hypothesis related to the primary efficacy endpoint is rejected. No further adjustments will be applied. Testing of all secondary efficacy endpoints will be exploratory.

### 8.5 Derived and computed variables

### 8.5.1 ACR response

For efficacy endpoints, ACR30 with absence of fever attributable to the disease, is defined as an improvement of  $\geq 30\%$  from baseline in at least 3 of any 6 variables listed below. Also, no more than 1 of the 6 variables may worsen by > 30% from baseline.

- 1. Physician global assessment of disease activity (VAS)
- 2. Patient/parent global assessment of overall well-being (VAS)
- 3. Number of joints with active arthritis
- 4. Number of joints with limitation of motion
- 5. Assessment of physical function (CHAQ/SHAQ)
- 6. CRP (mg/L)

Correspondingly, ACR50, ACR70 and ACR90 with absence of fever attributable to the disease, is defined for  $\geq$  50%, 70% and 90% response, respectively. Likewise, in these analyses, no more than 1 of the 6 variables may worsen by  $\geq$  30% from baseline.

Sustained ACR30 response include patients that achieved at least ACR30 response at Week 2, and further had at least ACR30 response at Week 4, Week 8 or Week 12, respectively.

#### 8.5.2 Absence of fever

Separate eCRF forms will specifically query whether fever was absent or present in the 24 hours preceding Week 1 or absent/present in the 7 days preceding Week 2.

Absence of fever at subsequent weeks (Week 4, 8 and 12) will be derived based on information recorded in the fever diary during the 7 days preceding each visit. The number of patients with

no missing data on fever will constitute the denominator for the percentage of patients with absence of fever during each week.

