6.5.1.6 Week 4 and Week 8 visits

The visits will be scheduled as close as possible to 24 hours after last IMP dose.

Assessments conducted at the visits are the ACR variables, physical examination including complete joint exam, global assessment of the patient disease related pain, vital signs, and concomitant medication. If any fever or rash attributable to the disease has occurred during the 7 days preceding the visit, this will be recorded. Data from the patient diary will support the evaluation.

Blood samples will be collected for central laboratory assessments, immunogenicity assessments and IL-1Ra/anakinra serum concentration assessments. Adverse events as well as number of days of absenteeism from school or work since previous visit (also recorded for guardians where appropriate) will be recorded. The patient diary will be reviewed to confirm

that instructions are followed and IMP covering the period until next visit will be dispensed. After all assessments have been performed at the visit the daily IMP administration can occur.

If the patient is on glucocorticoid treatment consider the possibility to taper if the patient has reached at least ACR50 response with no fever in the preceding 7 days. See Appendix 4 for suggested glucocorticoid tapering instructions.

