6.5.1.7 Week 12 visit

The visit will be scheduled as close as possible to 24 hours after last IMP dose.

Assessments conducted at the visit are the ACR variables, physical examination including complete joint exam, global assessment of the patient disease related pain, vital signs, and concomitant medication. If any fever or rash attributable to the disease has occurred during the 7 days preceding the Week 12 visit, this will be recorded. Data from the patient diary will support the evaluation.

Blood samples will be collected for central laboratory assessments, immunogenicity assessments, IL-1Ra/anakinra serum concentration assessments and exploratory inflammatory biomarkers. Inactive disease (see 6.5.4.5) will be evaluated. Adverse events as well as number of days of absenteeism from school or work since previous visit (also recorded for guardians where appropriate) will be recorded. The patient's diary will be reviewed. Finally all IMP should be collected from the patient and accounted for.

For patients enrolled in the repeated-dose PK sampling, this visit should be scheduled on the same day as the last dose of IMP administration is planned. For details regarding the blood sampling procedure and IMP administration see 6.5.6.1.

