6.5.1.9 Study Drug Discontinuation visit

The visit is performed if the investigator judges that a patient must discontinue study drug before the Week 12 visit. A Study Drug Discontinuation visit should be performed before standard of care treatment is initiated, when possible. If the study drug is discontinued on a scheduled visit, the assessments for the Study Drug Discontinuation visit should be performed instead of the assessments of the scheduled visit, unless the study drug is discontinued at the Week 12 visit.

Assessments conducted at the visit are the ACR variables, physical examination including complete joint exam, global assessment of the patient disease related pain, vital signs, and concomitant medication. If any fever or rash attributable to the disease has occurred during the 7 days preceding the Study Drug Discontinuation visit, this will be recorded. If this visit is performed before the Week 1 visit, fever and rash attributable to the disease during the 24-hours preceding the Study Drug Discontinuation visit will be recorded. Data from the patient diary will support the evaluation.

Blood samples will be collected for central laboratory assessments, immunogenicity assessments, IL-1Ra/anakinra serum concentration assessments and exploratory

inflammatory biomarkers. Inactive disease (see 6.5.4.5) will be evaluated. Adverse events, number of days of absenteeism from school or work since previous visit (for guardians where appropriate) as well as morning stiffness will be recorded. The reason for study drug discontinuation is recorded in the CRF. "Escape criteria" can be evaluated in the CRF. Finally, all IMP should be returned and accounted for.

Patients that discontinue study drug before the Week 2 visit should still return for a Week 2 visit according to original schedule of assessments. If the Study Drug Discontinuation visit is performed within 3 days prior to the Week 2 visit, the scheduled Week 2 visit should be omitted.

A final follow-up call will be conducted 4 weeks after the last IMP administration according to the assessments described for the Week 16_{Tel}.

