6.5.4.1.7 Fever

For endpoint evaluation in this study the definition of fever is $\geq 38.0^{\circ}\text{C}$ (100.4°F) and should be attributable to the disease as judged by the investigator.

Fever will be measured orally, under the tongue and using the same thermometer (provided for the study) throughout the study. The measurement and time point will be recorded in the patient's diary. Fever will be measured during the treatment period whenever there is a fever episode. In addition the patient will get a question daily in the diary asking if he/she experienced any fever episode that day.

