9.1 Case report form

A CRF is required and should be completed for each included patient. In this study electronic CRF will be used. The completed original CRFs are the sole property of Sobi and should not be made available in any form to third parties, except for authorized representatives of appropriate Regulatory Authorities, without written permission from Sobi.

It is the responsibility of the investigator to ensure completion and to review and approve all CRFs. CRFs must be signed electronically by the investigator. These signatures serve to attest that the information contained on these CRFs is correct. At all times, the investigator has final responsibility for the accuracy and authenticity of all clinical and laboratory data entered on the CRFs.

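### SAP 8.5.2 takes absence of fever at Weeks 4, 8 and 12 from the patient diary, which as described cannot show whether a fever was due to Still's disease

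*SAP*

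**What the plan says.** **Definition.** Protocol 6.5.4.1.7 sets a threshold of 38.0 °C and adds that the fever "should be attributable to the disease as judged by the investigator". SAP 3.3.1 repeats the threshold together with attribution, and SAP 8.5.1 carries attribution into the ACR30, 50, 70 and 90 definitions.

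**Recording at visits.** For Weeks 4 and 8, protocol 6.5.1.6 says: "If any fever or rash attributable to the disease has occurred during the 7 days preceding the visit, this will be recorded". For Week 12, protocol 6.5.1.7 says: "If any fever or rash attributable to the disease has occurred during the 7 days preceding the Week 12 visit, this will be recorded". Both sections give the diary a supporting role. Protocol 6.5.1.9 has a matching instruction for patients who stop study drug.

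**The diary.** Protocol 6.5.4.1.7 has the patient record temperature and time whenever a fever occurs, and continues: "In addition the patient will get a question daily in the diary asking if he/she experienced any fever episode that day". Protocol 9.2 lists rash, fever time and temperature, and dosing times. Protocol 9.3 names the diary as source data for fever.

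**The derivation.** SAP 8.5.2 uses eCRF forms for Weeks 1 and 2. For the later visits: "Absence of fever at subsequent weeks (Week 4, 8 and 12) will be derived based on information recorded in the fever diary". It mentions no step at which the investigator's judgement on cause enters.

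**Where the result is used.** ACR response combined with absence of fever, through Week 12, is a listed secondary endpoint (SAP 3.3.4). SAP 12.4.2 shows it in swimmer plots and tabulates absence of fever separately by visit.

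**The concern.** The definition has two parts: a temperature threshold and a judgement on cause. A diary of times, temperatures and yes/no answers can satisfy the first but not the second. A programmer who follows SAP 8.5.2 literally would count any recorded fever at or above the threshold, including one from an intercurrent infection.

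Such a patient would be shown as not fever-free at that visit. If the six ACR variables were otherwise met, the patient would also lose ACR response there. Sustained response under SAP 8.5.1 requires a Week 2 responder to respond again at Week 4, 8 or 12, so it inherits the error. With about a dozen patients, one such case is visible in any percentage or plot.

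**Working it through.** No figure in the plan needs to be reproduced. The check is a comparison of texts, followed by the size of one reclassified patient.

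**Step 1: what the definition needs against what the source holds.**

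| Element of endpoint fever | Required by | In the diary as described (protocol 6.5.4.1.7, 9.2)? |
|---|---|---|
| Temperature at or above 38.0 °C | Protocol 6.5.4.1.7; SAP 3.3.1 | Yes: temperature and time of each episode |
| Occurrence in the preceding 7 days | Protocol 6.5.1.6, 6.5.1.7 | Yes: daily question and dated episodes |
| Investigator's judgement that the disease is the cause | Protocol 6.5.4.1.7; kept as disease attribution in SAP 8.5.1 | No item described |

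The protocol obtains the third element at the visit. SAP 8.5.2 names only the diary for Weeks 4, 8 and 12. The definition in 8.5.1 and the derivation in 8.5.2 therefore do not meet at those visits.

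**Step 2: direction.** With a complete diary, every disease fever is also a diary fever, but not the reverse. Using diary fevers of any cause can therefore only lower the fever-free and response rates within an arm. The difference between arms can move either way, depending on which arm the misclassified patient is in.

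**Step 3: size of one patient.** SAP 4.2 expects at least 12 randomized patients at 2:1.

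- Anakinra: 12 × 2/3 = 8. One patient is 1/8 = 12.5 points.
- Placebo: 12 × 1/3 = 4. One patient is 1/4 = 25.0 points.

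One reclassified anakinra patient lowers the anakinra-minus-placebo difference by 12.5 points, and one placebo patient raises it by 25.0. In the fever table the step is larger if some patients lack fever data, because those with "no missing data on fever will constitute the denominator for the percentage of patients with absence of fever during each week".

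**Step 4: how often (assumed inputs, illustration only).** The documents give no rate of non-disease fever. Let q be the chance of one in a 7-day window, independent between patients, and n the number of patients who would otherwise be fever-free. The chance of at least one misclassification at a visit is 1 − (1 − q)^n.

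| q (assumed) | n = 6 (assumed) | n = 12 (upper limit at 12 patients) |
|---|---|---|
| 2 % | 11 % | 22 % |
| 5 % | 26 % | 46 % |
| 10 % | 47 % | 72 % |

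The answer depends heavily on both assumptions. It shows only that one case is not far-fetched, and the conclusion does not rest on it.

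**The case against.** The best defence is that SAP 8.5.2 names a data source and does not say that every diary fever counts whatever its cause. SAP 3.3.1 and 8.5.1 keep attribution, protocol 9.3 makes the diary the source for fever, and the diary is reviewed at each of these visits. On that reading the defined term is simply applied to diary readings. Part of this stands: the SAP does not declare an any-cause endpoint, and a reader should not infer that one is intended. But being the source for readings does not make the diary a source for the judgement on cause, and the derivation gives no other.

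The actual diary and eCRF screens are not in the documents, and protocol Appendix 5 has no separate row for a visit-level fever record. Whether attribution was captured at Weeks 4, 8 and 12 therefore cannot be confirmed. This stands, and the fix allows for it.

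Two stronger readings are tempting, and the documents do not support either.

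- *Weeks 1 and 2 are properly attributed and the later visits lose this.* SAP 8.5.2 describes the Week 1 and 2 forms only as asking whether fever was absent or present. The general clause in protocol 9.1, "It is the responsibility of the investigator to ensure completion and to review and approve all CRFs", does not show that those forms capture cause.
- *The fever denominator is an error because Week 2 counts missing fever as fever present.* Protocol 8.4.1 and SAP 8.2.1 pre-specify observed cases for other secondary endpoints, and the standalone Week 4-12 fever percentage is not a listed endpoint. A further column over all mITT patients would be optional.

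Finally, SAP 8.1 promises listings of all values contributing to a time point. With about 12 patients, a reader could probably trace a single decisive fever. That lessens the harm but does not repair the derivation.

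**Conclusion.** The point holds and is minor. The source stated in SAP 8.5.2 for Weeks 4, 8 and 12 does not deliver the disease-attributable fever that the protocol and SAP 8.5.1 require, and it replaces a visit record that the protocol calls for.

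The consequence is limited to secondary results: the Week 4-12 fever table, the fever part of Week 4-12 ACR response, and the sustained response built on it. These are plots and counts with no planned test, and SAP 8.4 treats all secondary testing as exploratory. A reader might infer that the main efficacy conclusion is exposed. It is not, because the primary endpoint is at Week 2 and the key secondary endpoints are at Week 1, and neither uses this derivation.

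The size that follows from the documents is 12.5 points (anakinra) or 25 points (placebo) per reclassified patient. It assumes exactly 12 patients split 8 and 4, all in the denominator. How many patients would be reclassified cannot be derived from the documents. The finding also assumes that the diary holds no more than the protocol describes.

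**What to change.** Before database lock and unblinding, amend SAP 8.5.2 so that absence of fever at Weeks 4, 8 and 12 comes from the investigator's visit record of disease-attributable fever (protocol 6.5.1.6 and 6.5.1.7), with the diary in support. Apply this to both the fever table and the fever part of ACR response.

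If the visit record was not captured, choose one of two fallbacks and state it in the SAP:

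- have investigators attribute the recorded diary fevers while still blinded; or
- label the Week 4-12 result any-cause fever and say that it departs from the protocol definition.

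The main change costs a few lines of SAP text and some reprogramming. Attribution of diary fevers is bounded: 12 patients × 3 visits = 36 seven-day windows at most, plus 3 per additional patient, and only windows with a recorded fever need review. Its drawback is retrospective judgement, which is why it must be done blind. Relabelling costs only wording, but gives up the defined endpoint at those visits.

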#### 8.5.3 JADAS27

The JADAS27 includes 4 measures: physician global assessment of disease activity, patient or parent global assessment of overall well-being, 27 active joint count, and CRP. The JADAS27 includes the following 27 joints: cervical spine, elbows, wrists, metacarpophalangeal joints (from first to third), proximal interphalangeal joints, hips, knees, and ankles.

JADAS27 is calculated as the sum of its four components, physician global assessment of disease activity converted to cm from the VAS (0=no activity, 10=maximum activity); patient global assessment of well-being converted to cm from the VAS (0=very well, 10=very poor); active joint count (0-27); and CRP. Prior to calculation CRP is truncated to a 0-10 scale according to the following formula: (CRP (mg/l) -10)/10. Before calculation, CRP values <10 mg/l are converted to 10 and CRP values >110 mg/l are converted to 110. The JADAS27 tool yields a global score of 0–57.

#### 8.5.4 Inactive disease

At the Week 12 visit and at the Study Drug Discontinuation visit, if applicable, the presence or absence of specific physical examination findings which are associated with Still's disease will be recorded to assess "inactive disease". Inactive disease is a composite of the following parameters: no joints with active arthritis, no fever, no rash, no serositis, no splenomegaly, no generalized lymphadenopathy attributable to Still's disease, CRP level within normal limits, physician's global assessment of disease activity score below 10 mm on a 100 mm VAS and a documented morning stiffness ≤15 minutes. The assessment of inactive disease is based on observed data for all parameters, with no imputation in case of missing information.

#### 8.5.5 Primary disease characteristics

Age at Still's disease diagnosis will be calculated based on date of birth and the date of Still's disease diagnosis as recorded on the Demography eCRF form.

Disease duration will be derived based on the Day 1 visit date and the date of Still's disease diagnosis, as recorded on the Demography eCRF form.

#### 8.5.6 Treatment exposure

The anakinra doses that will be evaluated are 2 mg/kg/day (max 100 mg/day) and 4 mg/kg/day (max 200 mg/day). The dose will be adjusted at baseline according to actual body weight (rounded to the nearest kg) and will remain the same throughout the study. The IMP administration will be supervised by the investigator or investigational site staff at the Day 1 visit and the exact time point for the administration will be recorded. At all other occasions when the

IMP is self-administered the patient will record the exact time point of the administration in the diary.

For each patient, the daily dose will be calculated as the total exposure (amount IMP (mg) given for the entire study) divided by the number of days on treatment.

The total treatment duration will be calculated as (date of last IMP - date of first IMP) +1.

### 8.5.7 Non-compartmental pharmacokinetic analysis

The serum anakinra concentration data from full PK sampling will be analyzed by NCA using SAS version 9.4. The following PK variables will be derived where applicable:

Cmax Observed maximum serum concentration of anakinra
 tmax Time to reach Cmax following dose injection
 AUClast Area under the serum concentration-time curve from time zero to the last quantifiable concentration (Clast), calculated by the linear up-log down trapezoidal method
 AUC0-24h,ss Area under the serum concentration-time curve during a dosage interval
 Vd/F Apparent volume of distribution following subcutaneous administration
 λz Terminal slope

 $t^{1/2}$  Apparent terminal half-life, calculated by  $0.693/\lambda z$ 

CL/F Apparent total clearance of drug from serum after subcutaneous

administration

The individual serum concentration data, and the actual time for anakinra administration and blood sampling will be used throughout the analyses. Samples with serum concentrations below the lower limit of quantitation (LLOQ) at early time-points will be treated as zero. Serum concentrations below the LLOQ appearing in the terminal samples will be omitted from the analysis.

Cmax and tmax will be derived directly from observed serum anakinra concentration values. AUClast will be calculated using the linear/log trapezoidal rule.

Extrapolation to 24h will be performed by adding the residual area up to 24h, ( $C_{8h, pred}/\lambda z$ - $C_{24h}$ ,  $_{pred}/\lambda z$ ), where  $\lambda z$  will be determined by linear regression of the log terminal part of the serum concentration versus time curve,  $C_{8h, pred}$  will be the predicted (according to the regression line) concentration at the time of the last sample (8h) and  $C_{24h, pred}$  will be the predicted (according to the regression line) concentration at 24h. CL/F will be calculated as Dose/AUC0-24h,ss and  $V_d$ /F will be calculated as  $\lambda z$  x CL/F.

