There is limited information about the PK of anakinra in SJIA patients, and no information about the PK of anakinra in AOSD patients. The PK of anakinra is however well characterized in healthy volunteers and RA patients. The bioavailability is high (~95%), t_{max} is about 6 hours and anakinra serum concentrations decline with a half-life of 4-6 hours following s.c. administration to RA patients. The exposure increases in approximate proportion to dose, accumulation is modest following once daily administration and approximately 80% of anakinra is eliminated by the kidney. In JIA patients trough anakinra concentrations were lower in the age group 3-6 years compared to older children and in 22 SJIA patients clearance was higher in children with a lower body-weight (28).

For a detailed description of anakinra characteristics, contraindications, warnings and precautions, adverse reactions and pharmaceutical properties, refer to the product information/monograph and the IB.

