6.5.6.1.1 Repeated-dose pharmacokinetics (pre-selected PK sites)

The repeated-dose PK of anakinra will be evaluated at 2 mg/kg/day (max 100 mg/day) and 4 mg/kg/day (max 200 mg/day). The planned target per dose level is 5 patients with disease onset <6 years, 5 patients with disease onset ≥ 6 to <16 years and 5 patients with a disease onset ≥ 16 years.

At the Week 12 visit, the IMP dose will be administered at the site and blood samples will be collected before the IMP administration and at 2, 4, 6 and 8 hours after IMP administration. The visit will be scheduled so that the IMP dose will be administered 24 hours (acceptance range 22-30 hours) after previous IMP dose the day before.

If exceeding maximum allowed blood volume for any patient, the samples at 4 and 6 hours may be replaced by a sample at 5 hours.

See Appendix 6 for a detailed description of the PK sampling procedure.

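### SAP 8.5.7 takes the terminal slope from samples that end at 8 h: half-life is overstated on every parameter set in the documents, and AUC0-24h,ss and CL/F are biased on most of them

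*SAP*

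**What the plan says.** Protocol 6.5.6.1.1 fixes the sampling: "blood samples will be collected before the IMP administration and at 2, 4, 6 and 8 hours after IMP administration". If blood volume is limited, "the samples at 4 and 6 hours may be replaced by a sample at 5 hours". The visit is timed so that "the IMP dose will be administered 24 hours (acceptance range 22-30 hours) after previous IMP dose", and Protocol 6.5.6 requires actual dosing and sampling times to be recorded.

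SAP 8.5.7 states that lambda-z "will be determined by linear regression of the log terminal part of the serum concentration versus time curve". Half-life is 0.693/lambda-z. For the rest of the dosing interval, "Extrapolation to 24h will be performed by adding the residual area up to 24h", with the 8 h and 24 h concentrations both predicted from the fitted line. CL/F is dose divided by the resulting AUC0-24h,ss. The section sets no minimum number of post-peak points, no rule on whether Cmax may enter the regression, no acceptance criterion, and no rule for a flat or rising slope. Its only qualifier is that variables are derived where applicable.

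On expected kinetics, Protocol 4.1 says that tmax "is about 6 hours and anakinra serum concentrations decline with a half-life of 4-6 hours following s.c. administration to RA patients". It also says: "There is limited information about the PK of anakinra in SJIA patients, and no information about the PK of anakinra in AOSD patients". SAP 14 lists the Week 12 parameters and plots individual profiles. SAP 17.1.1 makes the population PK/PD analysis optional.

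**The concern.** A terminal slope needs samples taken after absorption has essentially ended. With a peak at about 6 h, only the 6 h and 8 h samples are at or after it, and drug is still being absorbed. With a peak at 4.0-4.6 h there are two post-peak samples, still too early. A slope read there is too shallow, and the SAP carries it forward over the 16 h from 8 to 24 h.

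The pre-dose sample at Week 12 is an observed end-of-interval concentration at steady state. The non-compartmental analysis does not use it as the 24 h value and predicts that value instead.

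At stake are the listed half-life, AUC0-24h,ss and CL/F in a population whose PK the protocol describes as little known. The protocol presents a short half-life as a main advantage of the product, so a listed value several times too long would mislead.

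**Working it through.** **Model.** One compartment, first-order absorption, steady state, interval 24 h, k = CL/V:

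C(t) = [D·ka / (V·(ka - k))] × [e^(-k·t)/(1 - e^(-24k)) - e^(-ka·t)/(1 - e^(-24ka))]

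True AUC0-24h,ss = D/CL. The true terminal half-life is ln 2 divided by the smaller of k and ka. The SAP rule was applied to noise-free concentrations: linear-up/log-down AUC to 8 h, lambda-z from the last two or three samples, residual area (C8,pred - C24,pred)/lambda-z.

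**The protocol's own figure first.** At 50 kg and 100 mg, the Table 2 footnote gives CL/F = 0.847 × (50/70)^0.47 = 0.723 L/h. AUC is then 100,000 µg / 0.723 = about 138,300 ng·h/mL, against 18,776 in the table, about 7.4 times too high. The footnote does not reproduce Table 2, so both were used as separate parameter sets.

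**Parameter sets**
- A: Table 2 exposures with ka 0.38/h. At 50 kg, CL/F = 100,000/18,776 = 5.33 L/h, and V/F = 50.4 L matches the trough of 236. Steady-state tmax is 4.0-4.6 h over the three weights.
- B1: half-life 4, 5 or 6 h, with ka solved so that single-dose tmax is 6 h.
- B2: the same half-lives, with 6 h taken as the steady-state tmax.
- C: Table 2 footnote constants as printed.

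**Worked example, set A, 50 kg.** Concentrations at 0, 2, 4, 6 and 8 h are 236, 1131, 1355, 1302 and 1150 ng/mL.
- lambda-z (6-8 h) = ln(1302.1/1150.1)/2 = 0.0620/h, so half-life = 11.2 h. True: 6.6 h.
- AUC0-8h = 8,957. C24,pred = 1150 × e^(-0.0620×16) = 426, against a true 236.
- Residual area = (1150 - 426)/0.0620 = about 11,670. Total = about 20,625, or 20,625/18,776 = +10%.
- CL/F = 100,000/20,625 = 4.85 L/h, or -9%. Extrapolated share = 11,670/20,625 = 57%.

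**All sets, full schedule.** Half-lives are in hours, by weight (A, C: 20/50/100 kg) or by assumed half-life (B1, B2: 4/5/6 h).

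| Set | True half-life | 6-8 h slope: half-life | AUC error | 4-6-8 h slope: half-life | AUC error | Extrapolated share (6-8 h) |
|---|---|---|---|---|---|---|
| A | 5.0/6.6/7.8 | 8.2/11.2/13.8 | +9 to +10% | 11.3/16.9/22.6 | +19 to +21% | 52-59% |
| B1 | 4.3/5.0/6.0 | about 22 | +20 to +23% | 110/103/89 | +37 to +41% | 64% |
| B2 | 5.45/5.0/6.0 | 37-39 | +23 to +25% | slope has the wrong sign | not interpretable | 67% |
| C | 1.8/1.9/2.3 | 2.5/3.05/3.6 | -5 to +1% | 2.8/3.5/4.3 | -2 to +6% | 18-30% |

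The C shares are, for example, 14,739/81,110 = 18% at 20 kg and 30,732/101,014 = 30% at 100 kg. On the reduced schedule (5 and 8 h), half-life is 9.3/13.1/16.6 h in A and 33-34 h in B1, with AUC +12 to +13% and +26 to +29%.

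**Noise (assumed).** With 15% CV on each concentration, lambda-z is zero or negative in 12-32% of profiles in A and 38-45% in B1.

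**With the pre-dose value as C24h.** Set A, 50 kg: the 8-24 h log-trapezoid is 16 × (1150.1 - 236)/ln(1150.1/236) = 9,235. Total = 8,957 + 9,235 = 18,192, or -3%. Over the sets, full schedule, the AUC error is -3 to -4% (A), -5 to -6% (B1, B2) and -6 to -8% (C). The 8-24 h half-life is 5.4/7.0/8.4 h in A (about 1.1 times true), 6.9-7.7 h in B1, and 8.3-8.8 h against 5.0-6.0 h in B2 (up to 1.65 times true).

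**The case against.** **Direction of the AUC and CL/F errors.** A reader might infer that AUC0-24h,ss is always overstated and CL/F always understated. The documents do not support that. With the footnote constants the AUC error changes sign and stays within about -5 to +6%. Those constants do not reproduce Table 2, which weakens them, but the documents do not say which part of Table 2 is wrong. The extrapolated share also falls below half in that set. This objection stands.

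**The 6 h peak.** It comes from RA patients, and Table 2 exposures imply an earlier one. A reader might also take 37-39 h, or a rising 4-6-8 h slope, as the expected result. Both require 6 h to be a steady-state tmax, which Protocol 4.1 does not say. Read as a single-dose tmax, it gives about 22 h and a slope of the correct sign. This stands as a limit on size, not on the half-life direction.

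**The remedy is imperfect.** An 8-24 h half-life is still too long. With the footnote constants, the anchored AUC (-6 to -8%) is no better than the plan's. The assay measures endogenous IL-1Ra together with anakinra (Protocol 6.5.6.2), and any endogenous share weighs most at trough; the documents give no level. All of this stands and should be stated.

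**Small consequence.** SAP 4.2 expects at least 12 patients at 2:1, so about 8 on anakinra at that minimum. Only those at selected PK sites who reach Week 12 contribute. The parameters are listed, not tested, and SAP 14 does summarise troughs at each visit. This limits the importance but does not make the rule right.

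**Conclusion.** The concern holds for half-life without condition on the parameter set: wherever the slope is estimable, the 2-8 h samples give too long a value. With the 6-8 h slope it is about 22 h (6 h as single-dose tmax) to 37-39 h (6 h as steady-state tmax) against 4.3-6.0 h true. It is 1.6-1.8 times true on Table 2 exposures and 1.4-1.6 times true on the footnote constants.

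For AUC0-24h,ss and CL/F the bias is conditional. AUC is +20 to +25% with the documented tmax and half-life (CL/F about -17 to -20%), and +9 to +10% with two points or +19 to +21% with three on Table 2 exposures. It is close to neutral with the footnote constants.

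These figures assume a one-compartment model, steady state and noise-free data. With assay noise, a material share of profiles would give no usable slope, and the SAP has no rule for them. The point is worth correcting, but it is confined to secondary PK listings in few patients and does not touch the efficacy analyses.

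**What to change.** Amend SAP 8.5.7 as follows.

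1. Take the observed Week 12 pre-dose concentration as C24h when the previous dose was given 22-30 h earlier, using the recorded actual times.
2. Compute AUC0-24h,ss as AUC0-8h plus the log-trapezoid from the observed 8 h value to C24h, and CL/F as dose divided by that AUC.
3. Do not report a terminal half-life from the 2-8 h samples. If an 8-24 h half-life is listed, label it approximate and biased upward (about 1.1 times true on Table 2 exposures, up to about 1.65 times with tmax 6 h). Omit it when the pre-dose sample is missing or below LLOQ.
4. State the residual limits: AUC error of about -3 to -6% (-6 to -8% with the footnote constants), reliance on steady state and on a recorded previous-day dose, and the endogenous IL-1Ra in the assay.

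The cost is SAP wording and programming; no extra samples are needed.

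Two neighbouring items should be settled at the same time. SAP 8.5.7 multiplies CL/F by lambda-z to obtain V_d/F, which does not give a volume; CL/F divided by lambda-z does, and it inherits any error in lambda-z. The Table 2 footnote and the Table 2 values in Protocol 6.2.1 also need to be reconciled.
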